Prospective, randomized, controlled, single-centre study with two parallel-group, open-label trial Duration: 6 weeks of intervention with follow-up for 1 week. Participants will be randomly assigned in a 1:1 ratio to receive either HPTC or dHCAM treatment

Sample Size: 80 patients (40 per arm)

- i. Group A: 20 patients receiving HPTC treatment.
- ii. Group B: 20 patients receiving dHCAM treatment.

Eligibility Criteria

Inclusion criteria

- a. Subjects must be at least 18 years of age or older
- b. Presence of a Stage III or Stage IV pressure ulcer, as defined by the National Pressure Ulcer Advisory Panel
- c. Ulcer size between 5 cm² and 25 cm²
- d. Ulcer duration of at least 4 weeks prior to enrolment
- e. The subject must agree to attend the twice-weekly/weekly study visits required by the protocol
- f. The subject must be willing and able to participate in the informed consent process
- g. Adequate blood supply to the affected area, confirmed by clinical assessment

Exclusion criteria

Potential subjects meeting any of the following criteria will be excluded from enrolment.

- a. A subject known to have a life expectancy of <6 months
- b. Presence of infection in the ulcer requiring systemic antibiotics.
- c. Known allergy to components of HPTC or dHCAM.
- d. Participation in another wound care study within the last 30 days.
- e. A subject with autoimmune or connective tissue disorders.
- f. Women who are pregnant or considering becoming pregnant within the next 6 months and those who are breast feeding.
- g. History of autoimmune disease, immunosuppressive therapy, malignancy, or uncontrolled diabetes (HbA1c >10%).

Study treatment

The treatment phase will begin with a series of assessments designed to confirm the patients' continued eligibility. Subjects who continued to meet study inclusion criteria after the screening period were randomized to one of two groups:

- 1. HPTC
- 2. dHCAM

Interventions

Wound Preparation - Prior to application, wounds will be debrided to remove necrotic tissue and cleansed with a standard saline solution.

Application Protocol:

- a. HPTC Group: Participants will receive standard wound care plus application of HPTC
- b. dHCAM Group: Participants will receive standard wound care plus application of dHCAM

All participants will receive standard care measures, including:

- a. Regular repositioning to alleviate pressure.
- b. Nutritional support to address deficiencies.
- c. Management of comorbid conditions.

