Randomization and Blinding

Patients will be randomized 1:1 to the HPTC or dHCAM group using a computer-generated randomization sequence. Due to the nature of the interventions, blinding of participants and clinicians is not feasible. However, outcome assessors and data analysts will be blinded to group assignments.

Data Collection and Monitoring

- a. Baseline data: Demographics, medical history, ulcer characteristics.
- b. Weekly follow-ups: Wound measurements (photographic documentation), assess healing progress, record adverse events and patient-reported outcomes.
- c. End-of-Study Visit (Week 5): final wound assessment, collect patient feedback on treatment experience.
- d. Data entry and monitoring will be managed using an electronic data capture system.
- e. Regular monitoring will ensure adherence to the study protocol and address any compliance issues.

Statistical Analysis

Descriptive statistics for baseline characteristics. Statistical analysis was performed using SPSS version 26.0 (IBM Corp., Armonk, NY). Continuous variables were presented as mean \pm standard deviation or median (interquartile range) based on distribution normality assessed by Kolmogorov-Smirnov test. Categorical variables were presented as frequencies and percentages.

Between-group comparisons for continuous variables were performed using independent t-test or Mann-Whitney U test as appropriate. Chi-square test or Fisher's exact test was used for categorical variables. Time-to-event analysis was performed using Kaplan-Meier survival curves with log-rank test. Repeated measures ANOVA was used to analyse wound size changes over time.

Statistical significance was set at p<0.05. All analyses were performed on intention-to-treat basis with last observation carried forward for missing data.

Sample Size Calculation

Sample size calculation was based on expected difference in wound closure rates between groups. Assuming 85% closure rate in HPTC group versus 65% in dHACM group, with 80% power and 5% significance level, 38 patients per group were required. To account for 10% dropout rate, 40 patients per group were enrolled.

Study completion

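### Stage III and IV ulcers of 5 to 25 cm² are admitted, but the plan names no stratification and no baseline adjustment, which costs precision and leaves a chance imbalance uncorrected

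*Combined protocol and SAP*

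**What the plan says.** Eligibility Criteria, inclusion criterion b: "Presence of a Stage III or Stage IV pressure ulcer, as defined by the National Pressure Ulcer Advisory Panel". Criterion c: "Ulcer size between 5 cm² and 25 cm²".

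Randomization and Blinding: "Patients will be randomized 1:1 to the HPTC or dHCAM group using a computer-generated randomization sequence". No strata, blocks or minimisation are named there or elsewhere.

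Statistical Analysis names four families of comparison, none with a covariate or stratification factor:

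- continuous outcomes: "Between-group comparisons for continuous variables were performed using independent t-test or Mann-Whitney U test as appropriate"
- categorical outcomes: "Chi-square test or Fisher's exact test was used for categorical variables"
- time to event: "Time-to-event analysis was performed using Kaplan-Meier survival curves with log-rank test"
- wound size by visit: "Repeated measures ANOVA was used to analyse wound size changes over time"

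Data Collection and Monitoring lists ulcer characteristics among the baseline data. The Statistical Analysis section gives baseline characteristics a descriptive role only. Percentage wound area reduction, a primary outcome, does use baseline area, as its denominator.

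**The concern.** Depth stage and starting area can reasonably be expected to affect how far an ulcer shrinks, and whether it closes, in 6 weeks. Both must be known before randomisation to apply criteria b and c. A plan that neither balances nor adjusts for them gives something up in two ways.

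- **Precision.** Outcome variation due to stage and area stays in the error term and widens the confidence interval in every trial, balanced or not.
- **Conditional bias.** If one arm happens to receive more Stage IV ulcers, part of the observed difference reflects case mix, and no planned analysis separates the two. In a single-centre trial of this size, such imbalances are not rare.

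**Working it through.** **Inputs from the documents.** Area limits 5 and 25 cm² (ratio 25/5 = 5). Allocation 1:1. 40 per arm (Study Design; Sample Size Calculation), although the group list under Study Design gives 20 per arm. Closure 85% versus 65%, a planned difference of 20 points. The plan gives no figure for stage mix, imbalance or variance explained, so there is none to reproduce.

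**Assumptions, not in the documents.** Stage IV share 30-50%. SD of percentage area reduction 25 points. Difference in mean reduction between stages g = 15-20 points. Difference in closure between stages 30 points.

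**Step 1: how often the arms differ.** Under simple randomisation, take the Stage IV counts as independent Binomial(n, p). The SD of the difference in share is √(2p(1−p)/n). At n = 40 this is √(0.50/40) = 11.2 points for p = 0.5 and √(0.42/40) = 10.2 points for p = 0.3. Exact probabilities:

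| Per arm | Stage IV share | Differ by ≥15 points | Differ by ≥20 points |
|---|---|---|---|
| 40 | 50% | 21.9% | 9.3% |
| 40 | 30% | 17.9% | 6.7% |
| 20 | 50% | 43.0% | 26.8% |
| 20 | 30% | 38.7% | 22.6% |

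**Step 2: false-positive rate given an imbalance (area reduction, t-test, 40 per arm, half Stage IV).** The shift is g × d, where d is the imbalance. The within-stage variance is W = 625 − g²/4. Once the stage counts are fixed, the difference in means has SD s = √(2W/40). The t-test's own standard error also contains the stage variance: SE² = Σ(W + g²q(1−q))/40 over the two arms, where q is the arm's Stage IV share. The rejection rate is approximately P(Z > (1.96·SE − gd)/s) + P(Z > (1.96·SE + gd)/s).

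| g | Stage IV counts | Shift gd | s | SE | Formula | Simulated t-test |
|---|---|---|---|---|---|---|
| 15 | 23 v 17 | 2.25 | 5.33 | 5.58 | 5.8% | 5.8% |
| 15 | 24 v 16 | 3.00 | 5.33 | 5.58 | 7.3% | 7.2% |
| 20 | 23 v 17 | 3.00 | 5.12 | 5.58 | 6.4% | 6.2% |
| 20 | 24 v 16 | 4.00 | 5.12 | 5.57 | 9.0% | 8.8% |

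The simulation used 200,000 trials per row. Reading the SD of 25 as within-stage instead gives 5.7-8.4%. So the range is about 6-9%. ANCOVA with stage as a covariate stays at about 5% whatever the imbalance.

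**Step 3: precision.** With half the ulcers Stage IV, the variance explained by stage is (g²/4)/total variance. With total SD 25, this is 56.25/625 = 9% for g = 15 and 100/625 = 16% for g = 20. With 25 as the within-stage SD, it is 56.25/681.25 = 8% and 100/725 = 14%. Adjustment is worth a factor 1/(1 − R²) in sample size: 1/(1 − 0.083) = 1.09 to 1/(1 − 0.16) = 1.19.

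**Step 4: closure.** The shift is 0.15 × 30 = 4.5 points to 0.20 × 30 = 6 points, or 23-30% of the planned 20. The standard error of the closure difference is √(0.85×0.15/40 + 0.65×0.35/40) = 9.4 points. The shift is therefore 4.5/9.4 = 0.48 to 6/9.4 = 0.64 of one standard error.

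**The case against.** The strongest reply is that randomisation already protects the test. That stands. Over all possible allocations the unadjusted t-test keeps about 5% type I error, because its standard error includes the variation due to stage. A reader might infer that the plan is systematically biased or that its overall error rate is inflated. Neither follows.

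Further limits also stand:

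- **Size of the conditional rate.** Adding the shift to a unit-variance z statistic suggests 7-11%. That is too high, because the t-test's standard error exceeds the conditional SD (Step 2).
- **Typical imbalance.** At 40 per arm and half Stage IV, the mean absolute imbalance is 8.9 points. Under the assumed 30-point gap that moves closure by 0.089 × 30 = 2.7 points. Imbalances of 15 points or more are the minority case.
- **Baseline area.** It might seem that area is recorded and then ignored. It is not: percentage reduction divides by it, which removes part of the size effect. It removes neither the effect of stage nor any dependence of closure on starting size.
- **Larger efficiency gains.** Explaining 30% of the variance would be worth 1/0.70 = 1.43, or 43% more patients. Stage alone does not reach that under these assumptions, and nothing in the documents supports the large further contribution from area that it would need.
- **Prognostic premise.** The documents do not say that stage and area predict healing, let alone that they are the main predictors.
- **Silence on stratification.** The protocol does not say that the list is unstratified. It may be stratified and not described.

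None of this supplies a reason to leave out prespecified adjustment.

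**Conclusion.** The point holds as one of precision and of protection against a chance imbalance; the planned tests are not invalid. It is worth acting on because the remedy uses data already collected. At 40 per arm, a Stage IV imbalance of 15 points or more would arise in about 18-22% of trials, and of 20 points or more in about 7-9%. At 20 per arm, which the group list also gives, these become about 39-43% and 23-27%. Given an imbalance of 15-20 points, the t-test's false-positive rate for area reduction is about 6-9%, and the closure difference moves by 4.5-6 points, about half to two-thirds of its standard error. Adjusting for stage is worth roughly 9-19% more patients for area reduction.

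The absence of any stated stratification or adjustment is clear from the text. The sizes rest on the assumed stage mix, SD and stage gaps, and would shrink if stage matters less than assumed.

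**What to change.** Before any group data are seen, prespecify:

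- **Percentage area reduction:** ANCOVA with treatment, stage (III or IV) and log baseline area.
- **Closure:** a risk difference standardised from a logistic model with the same two covariates.
- **Time to closure:** a log-rank test stratified by stage.

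Keep to these two covariates. At the planned closure rates, 40 × 0.15 + 40 × 0.35 = 20 patients would not close, too few for a long covariate list. Choosing covariates after an imbalance has been seen would be open to challenge, so the timing matters.

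If enrolment has not begun, also stratify the randomisation list by stage, with varied block sizes because clinicians are unblinded. The documents mix future and past tense about enrolment, so the sponsor must say which applies. If the list is already stratified, the protocol should state the factor and the analysis should include it. The conflict between 40 and 20 per arm should be resolved in the same revision.

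The cost is a revised list where still possible, a short paragraph of analysis text and a little more analysis work. No new data are needed. Incomplete blocks may leave the arm sizes one or two apart.

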Title: Treatment of Pressure Ulcers using Biological Skin Substitutes: A Comparison of Type-I Collagen and Amnion/Chorion Membranes

NCT: NCT06853210

Date: 26/07/2025

Background

Pressure ulcers, also known as decubitus ulcers or bedsores, are localized injuries to the skin and underlying tissue resulting from prolonged pressure. They are prevalent in individuals with limited mobility, such as the elderly and those with spinal cord injuries, particularly in long-term care settings. Effective management of pressure ulcers is crucial to prevent complications and improve patient outcomes, includes pressure relief, wound care, and advanced therapies such as bioengineered skin substitutes. Management of pressure sores is crucial due to their association with increased morbidity, healthcare costs, and reduced quality of life. This study aims to evaluate the efficacy of two treatment modalities: Type-I Collagen-based Skin Substitute (HPTC) vs. Dehydrated Human Amnion/Chorion Membrane (dHCAM) in promoting the healing of pressure ulcers. While both products are used in wound management, direct comparative studies evaluating their efficacy in treating pressure ulcers are limited.

MATERIALS AND METHODS

This prospective, randomized, controlled, open label, two parallel group, single-centre clinical trial will be conducted at a tertiary care hospital, in India, specializing in wound care and reconstructive surgery. The study protocol was approved by the Institutional Ethics Committee (Approval Number: AIMS/IEC/012/2025) and pre-registered with the ClinicalTrials.gov (NCT06853210). All procedures will be performed in accordance with the Declaration of Helsinki and Good Clinical Practice guidelines. All participants or guardians will be provided informed consent.

Outcome Measures

Primary Outcome:

- a. Percentage Wound Area Reduction.
- b. Histopathological Parameters
 - i. Vascular Infiltration
 - ii. Neo-epithelialization
 - iii. Fibroblast Activity
 - iv. Capillary Density
 - v. Inflammatory Response
 - vi. Collagen Deposition

Secondary Outcomes:

- a. Complete Wound Closure Rates (defined as 100% epithelialization).
- b. Wound Size Progression Over Time 7 weeks

- c. Number of Reapplications
- d. Incidence of treatment-related adverse events (e.g., infection, allergic reactions)
- e. Quality of Life Improvement
- f. Patient Satisfaction Scores

Study Design

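### Quality-of-life improvement is a secondary outcome, but no quality-of-life score is scheduled before treatment, so change from baseline cannot be derived from the schedule as written

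*Combined protocol and SAP*

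**What the plan says.** The combined protocol and SAP names "Quality of Life Improvement" as secondary outcome e under Outcome Measures. It gives no instrument, no time point and no definition of improvement.

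Data Collection and Monitoring assigns data to visits:

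- Baseline: "Baseline data: Demographics, medical history, ulcer characteristics".
- Weekly: "Weekly follow-ups: Wound measurements (photographic documentation), assess healing progress, record adverse events and patient-reported outcomes".
- Final: "End-of-Study Visit (Week 5): final wound assessment, collect patient feedback on treatment experience".

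The Study treatment section mentions assessments before randomisation but gives them one purpose: "The treatment phase will begin with a series of assessments designed to confirm the patients' continued eligibility".

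For analysis, the Statistical Analysis section states: "Between-group comparisons for continuous variables were performed using independent t-test or Mann-Whitney U test as appropriate". It gives no baseline-adjusted model for quality of life. Missing data are covered by one sentence: "All analyses were performed on intention-to-treat basis with last observation carried forward for missing data".

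**The concern.** An improvement on a status questionnaire is a later score set against a starting score. The schedule places patient-reported data after treatment has begun and leaves them out of the baseline list. A site working from this text would have no reason to collect the starting score.

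Two things are at stake. The outcome as named could not be reported as a change from before treatment. The comparison of arms would also lose the precision that a baseline covariate gives. Both concern one of six secondary outcomes, and the sample size was not based on it.

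**Working it through.** **Reading the sections together.** The plan states no figure on this point, so the first check is whether any section supplies a pre-treatment score.

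1. Outcome Measures asks for improvement, which for a status questionnaire needs a starting value.
2. The baseline list has three categories, none of them patient-reported. It does cover the ulcer, so wound-area reduction has its starting value. Quality of life does not.
3. The weekly item is the first to mention patient-reported outcomes. A change measured from the first weekly score would start after treatment had begun, in participants who know their allocation (Randomization and Blinding). It would not be change from before treatment.
4. The final visit collects feedback on the treatment experience. That fits the satisfaction outcome, which needs no starting value.
5. The pre-randomisation assessments are described only as an eligibility check.
6. Carrying the last observation forward fills later gaps. It cannot create an earlier value.

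No section supplies the score.

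**What a baseline score would be worth (illustration only).**

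Inputs:

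- 80 patients, 40 per arm, from the Study Design and Sample Size Calculation sections. Study Design also lists 20 per group; that conflict is separate, and the variance ratios below do not depend on it.
- Significance level 0.05 from Statistical Analysis; two-sided is assumed.
- Power of 80%, as in the plan's own sample size calculation.
- Baseline-to-follow-up correlation ρ. The documents give none; 0.3 to 0.7 is assumed, with equal standard deviations (SD) at both times.

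Variance of the treatment comparison, relative to follow-up scores alone (= 1):

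- ANCOVA: 1 − ρ²
- Change scores: 2(1 − ρ)

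Equivalent number of patients = 80 / relative variance.

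| ρ | ANCOVA variance | Equivalent patients | Change-score variance | Equivalent patients |
|---|---|---|---|---|
| 0.3 | 1 − 0.09 = 0.91 | 80/0.91 ≈ 88 | 2 × 0.7 = 1.4 | 80/1.4 ≈ 57 |
| 0.5 | 1 − 0.25 = 0.75 | 80/0.75 ≈ 107 | 2 × 0.5 = 1.0 | 80/1.0 = 80 |
| 0.7 | 1 − 0.49 = 0.51 | 80/0.51 ≈ 157 | 2 × 0.3 = 0.6 | 80/0.6 ≈ 133 |

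Detectable difference at 40 per arm, in SD units, normal approximation:

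- Follow-up scores alone: (1.960 + 0.842) × √(2/40) = 0.63.
- ANCOVA: multiply by √(1 − ρ²), giving 0.60, 0.54 and 0.45 at ρ = 0.3, 0.5 and 0.7.
- Change scores: multiply by √(2(1 − ρ)), giving 0.74, 0.63 and 0.49.

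Power for an assumed true difference of 0.5 SD is 61% from follow-up scores alone and 65%, 73% and 88% with ANCOVA.

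The method matters as much as the extra measurement. Change scores beat follow-up scores only when 2(1 − ρ) < 1, that is, when ρ > 0.5. Adding a baseline questionnaire and then applying the planned unadjusted test to the change would bring no gain at ρ = 0.5 and a loss at ρ = 0.3.

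**The case against.** The strongest reply is that the data-collection section is a short summary, not a full schedule of assessments. The histopathological parameters are a primary outcome, yet no visit lists a biopsy or histology. The number of reapplications is not listed either. Absence from such a list is weak evidence that a score will not be collected, and a case report form may hold more. This stands as a limit on the claim: the documents show that no baseline score is specified, not that none will be taken. It does not remove the point, because the text does allocate patient-reported outcomes to visits and leaves out the one visit where improvement needs them.

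A second reply is that the instrument is unnamed. A transition item, which asks whether the patient is better, the same or worse than before, reports improvement without a starting score. That is correct, so the point is confined to status questionnaires.

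A reader might infer something stronger: that the outcome is impossible, that the quality-of-life data are lost for good, or that chance imbalance at baseline would invalidate the comparison. The documents do not support this. Weekly patient-reported scores are planned, and comparing them between randomised arms is valid; the test's error rate already allows for chance imbalance. A score is beyond recovery only for patients already treated, and the text mixes past and future tense, so it does not settle how many there are. Nor would a baseline score remove reporting bias during open-label follow-up, so the lack of blinding does not strengthen the case.

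**Conclusion.** The point holds in a limited form. Followed as written, the schedule gives no pre-treatment quality-of-life score, so change from before treatment cannot be derived for a status questionnaire. A comparison of follow-up scores between arms would stay valid but be less precise.

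The loss is the 9% to 49% variance reduction that ANCOVA would bring at a correlation of 0.3 to 0.7, or about 88 to 157 equivalent patients instead of 80. That range rests wholly on the assumed correlation and on using ANCOVA. The absence of a starting value depends on no assumed number. The consequence is minor because the outcome is secondary and did not drive the sample size, but the correction is cheap.

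**What to change.** - Name the quality-of-life questionnaire and add it to the baseline visit, the same one as at follow-up, completed before allocation is revealed.
- Define the outcome as the between-arm difference in score at the final visit, estimated by ANCOVA with the baseline score as covariate. Do not use an unadjusted test on change.
- State which week the final visit is. Data Collection and Monitoring puts it at Week 5, while Study completion refers to 6 weeks after the first treatment visit; the two must be reconciled.
- For patients already treated without a baseline score, report the outcome as quality of life at the final visit, and do not describe it as improvement.

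Cost: one short questionnaire per patient at a visit that already takes place, and one line of analysis text. No stated figure in the plan changes.

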Patients will complete the study 6 weeks after the first treatment visit. In addition, if, patients whose study ulcer closes prior to the 6-week visit will be considered as having completed the study. Complete healing of the study ulcer is defined as 100% re-epithelialization without drainage. At any point during the treatment period, patients can refuse to participate or withdraw from the study without prejudice. If a patient withdraws from the study, their last available wound measurement will be carried forward and used to calculate change in wound size and their final outcome

Ethical Considerations

- i. Approval will be obtained from the Institutional Ethics Committee.
- ii. Adherence to the Declaration of Helsinki and Good Clinical Practice (GCP) guidelines.
- iii. Informed and written consent will be obtained from all participants.
- iv. Adverse events will be monitored and reported.
- v. Participants may withdraw at any time without penalty.
- vi. Dissemination of Results
- vii. Findings will be submitted to peer-reviewed journals and presented at relevant conferences.

Timeline

Recruitment: 1 months Intervention: 3 months

Data analysis and reporting: 1 months

Potential Implications

This study aims to provide direct comparative data on the efficacy of HPTC versus dHACM in the treatment of pressure sores. The findings could inform clinical decision-making and potentially lead to improved patient outcomes in wound care management of pressure sores.

References:

- 2. Berhane, C. C., Brantley, K., Williams, S., Sutton, E., & Kappy, C. (2019). An evaluation of dehydrated human amnion/chorion membrane allografts for pressure ulcer treatment: a case series. *Journal of Wound Care*, 28(Sup5), S4–S10. https://pubmed.ncbi.nlm.nih.gov/31067170/
- 3. Vecin, N. M., & Kirsner, R. S. (2023). Skin substitutes as treatment for chronic wounds: current and future directions. *Frontiers in Medicine*, 10, 1154567. https://www.ncbi.nlm.nih.gov/pmc/articles/PMC10498286/
- 4. Helicoll® Clinical Study Publications. [https://helicoll.com/clinical-studies/]
- 5. A Randomized Controlled Clinical Trial Comparing the Use of High-Purity Type I Collagen Matrix (HPTC) and Dehydrated Human Amnion/Chorion Membrane (dHACM) Allografts in the Management of Diabetic Foot Ulcers.

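### The final wound assessment is set at Week 5, although the plan elsewhere runs to 6 or 7 weeks, and no analysis week is named for percentage wound area reduction or closure

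*Combined protocol and SAP*

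**What the plan says.** These statements bear on when a patient's last measurement is taken:

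- Data Collection and Monitoring, item c: "End-of-Study Visit (Week 5): final wound assessment, collect patient feedback on treatment experience".
- Data Collection and Monitoring, item b: "Weekly follow-ups: Wound measurements (photographic documentation), assess healing progress, record adverse events and patient-reported outcomes". No last week is given.
- Study Design: "Duration: 6 weeks of intervention with follow-up for 1 week".
- Study completion: "Patients will complete the study 6 weeks after the first treatment visit". It adds that "patients whose study ulcer closes prior to the 6-week visit will be considered as having completed the study".
- Outcome Measures, secondary outcome b: "Wound Size Progression Over Time 7 weeks".

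Primary outcome a reads only "Percentage Wound Area Reduction", with no week. Complete closure (secondary outcome a) has no week either, and Sample Size Calculation attaches none to its 85% and 65% closure rates. Statistical Analysis lists the tests (t-test or Mann-Whitney for continuous variables, chi-square or Fisher's exact for categorical ones) without a timepoint. Randomization and Blinding states that "outcome assessors and data analysts will be blinded to group assignments".

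**The concern.** The schedule gives three different ends of study, and the endpoint definitions do not say which one counts. Two consequences are possible, and they exclude each other.

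**(A) The Week 5 line governs.** The final wound measurement is taken while the stated intervention is still running, and an outcome defined to 7 weeks is never observed. Measurements not taken at weeks 6 and 7 cannot be recovered.

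**(B) Weekly measurement continues past Week 5**, as item b and the reference to a 6-week visit suggest. Nothing is lost, but weeks 5, 6 and 7 can each be defended from the protocol's own text as the analysis week for a primary outcome. If that choice is made after results are seen, the false-positive rate exceeds 5%.

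The handling of early closers adds to this. They count as completed, but the plan does not say whether their weekly assessments go on to the analysis week.

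**Working it through.** **Step 1: the stated weeks side by side**

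| Section | What it fixes | Week |
|---|---|---|
| Data Collection and Monitoring, item c | End-of-study visit, final wound assessment | 5 |
| Study completion | End of participation, 6-week visit | 6 |
| Study Design | Intervention plus follow-up | 6 + 1 = 7 |
| Outcome Measures, secondary b | Wound size progression | 7 |

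Study Design and the secondary outcome agree, since 6 + 1 = 7. Week 5 is 6 − 5 = 1 week before the end of intervention and 7 − 5 = 2 weeks before the end of follow-up. Completion at 6 weeks leaves out the follow-up week.

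**Step 2: what consequence (A) loses.** A weekly series over weeks 1 to 7 has 7 post-baseline points. Stopping at Week 5 leaves 5 of 7; stopping at 6 weeks leaves 6 of 7.

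**Step 3: search for an analysis week.** Outcome Measures, Statistical Analysis and Sample Size Calculation name none. Study completion says when a patient finishes and mentions a final outcome for withdrawals, but does not say at which week that outcome is taken.

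**Step 4: size of consequence (B) for wound area.** The documents give no week-to-week correlation and no closure pattern, so these models are assumptions. All use 40 per arm, no true difference and two-sided p<0.05, and take the smallest p-value over weeks 5, 6 and 7. Monte Carlo error is about 0.1 percentage point.

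*Unbounded normal values, first-order autoregressive, 50,000 trials* (any single week gave 4.8–5.2%):

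| Adjacent-week correlation | t-test | Mann-Whitney |
|---|---|---|
| 0.80 | 10.5% | 10.8% |
| 0.90 | 8.7% | 8.9% |
| 0.95 | 7.7% | 7.9% |
| 0.98 | 6.7% | 6.9% |

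*Values capped at 100%.* Percentage reduction at week w is min(100, 100·w/T), where T is closure time, with 65%, 75% or 85% of ulcers closed by week 6 in both arms:

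| Distribution of T | Trials | Adjacent-week correlation | t-test (65/75/85%) | Mann-Whitney (65/75/85%) |
|---|---|---|---|---|
| Exponential | 100,000 | 0.97–0.98 | 6.6 / 7.0 / 6.7% | 7.5 / 8.4 / 9.2% |
| Lognormal, log-SD 0.5 | 50,000 | 0.94–0.96 | 7.5 / 7.5 / 7.1% | 8.7 / 9.5 / 10.5% |

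*Only two adjacent weeks open to choice (5–6 or 6–7):* 6.0–8.1% in the normal model; in the capped model, 5.4–6.4% (t-test) and 6.3–8.1% (Mann-Whitney).

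**Step 5: size of consequence (B) for closure.** Exponential T, 200,000 trials, 65/75/85% closed by week 6 in both arms:

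| Test | Week 6 alone | Best of weeks 5–7 |
|---|---|---|
| Chi-square, uncorrected | 4.9 / 5.0 / 5.4% | 9.3 / 9.5 / 10.7% |
| Fisher's exact | 2.8 / 2.8 / 2.6% | 5.6 / 5.6 / 5.1% |
| Chi-square, continuity-corrected | 2.8 / 2.6 / 1.9% | 5.6 / 5.0 / 4.0% |

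**Step 6: does the week change the expected closure effect?** Assume a constant hazard with 85% and 65% reached at week 6. Closure at week w is then 1 − (1 − p)^(w/6).

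| Week | p = 0.85 | p = 0.65 | Difference |
|---|---|---|---|
| 5 | 0.794 | 0.583 | 0.211 |
| 6 | 0.850 | 0.650 | 0.200 |
| 7 | 0.891 | 0.706 | 0.185 |

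The estimated rates move with the week, but the difference between arms changes little.

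**The case against.** The best defence is that Study completion supplies a default. It ends participation at 6 weeks and refers to a 6-week visit and a final outcome, so a reader could infer week 6. That is a fair inference, but it says when a patient finishes, not when an endpoint is analysed, and the Week 5 line contradicts it. Counting weeks from zero might bring Week 5 close to the sixth week. No such numbering is defined, though, and it would still not reach week 7.

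Second, consequence (B) is conditional. Nothing in the plan announces a choice among weeks, and the three-week figures require week 7 to be measured, which Study completion contradicts. The 10.5% t-test figure needs a correlation of 0.80, whereas the capped models imply 0.94–0.98 and give 6.6–7.5%. These points stand and limit the size of (B). Analyst blinding also lowers the risk without removing it, because p-values can be compared across weeks between coded groups.

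Third, last observation carried forward applies to all analyses. If an early closer's later visits count as missing, closure and 100% reduction carry forward to any later week. That narrows the gap for early closers. However, the explicit rule in Study completion covers withdrawals only, and a reopened ulcer would go unseen.

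Fourth, repeated measures ANOVA uses the whole series, so choosing a week matters less for wound size over time. Its last time point is still undefined.

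**Conclusion.** The concern holds. The current text gives three incompatible ends of study (5, 6 and 7 weeks), and neither percentage wound area reduction nor closure has an analysis week. That conclusion rests on the documents alone. Followed as written, the Week 5 line takes the final measurement 1 week before the stated intervention ends and leaves 5 of 7 weekly points.

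If measurement continues instead, the inflation for the primary outcome is moderate and depends on the model: about 7–10% with a t-test and about 7–11% with Mann-Whitney for the best of three weeks, and about 5.4–8.1% for two adjacent weeks. For closure it matters only with an uncorrected chi-square test (9.3–10.7%). With Fisher's exact test (5.1–5.6%) or a continuity correction (4.0–5.6%) the error stays about nominal. The expected closure difference moves only from about 21 to 18 points.

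Correction is needed because a primary outcome has no timepoint and the schedule that might supply one contradicts itself. The case does not depend on the simulated rates.

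**What to change.** - Reconcile Study Design, Data Collection and Monitoring, Study completion and secondary outcome b on the end-of-study week. The length of treatment is for the sponsor to settle.
- Name one analysis week for percentage wound area reduction and complete closure, before any comparison between groups. The 6-week visit already in the text is one candidate.
- Place the final wound assessment at that week, state the last weekly measurement, and label any later value as follow-up.
- State the week to which the closure rates in Sample Size Calculation refer, and the week to which last observations are carried forward.
- State whether patients whose ulcer closes early continue the planned weekly assessments to the analysis week.

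The cost is protocol wording and, if early closers stay in assessment, a few more visits for them.
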